2.1.3 Secondary Endpoints

There are no formal tests of hypotheses associated with secondary endpoints 1-3.

1. Pacing threshold, sensing and impedance measurements for the Protego DF4 lead through 5 years post-implant.
2. Shock impedance for the Protego lead through 5 years post-implant.
3. Adverse event rates for protocol defined, CEC adjudicated AEs excluded from primary safety endpoints 1 and 2, through 5 years post-implant.

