2.3.1 Attrition

For the sample size calculation, a maximum loss to follow-up of 10% per year (41% over 5 years) was assumed. The loss to follow-up rate encompasses all causes for subjects to be exited from the registry, including death, device explants, subject directed withdrawals, physician-directed withdrawals, and loss of contact with the subject.

Table 3: Primary Safety Endpoints Sample Sizes

	Primary Safety Endpoint 1	Primary Safety Endpoint 2
Sample Size of Evaluable Subjects	750 subjects	1000 subjects
Total Adjusted for Attrition	1271 subjects	1694 subjects

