2.4.1 Endpoint Analysis

Primary safety endpoint 1 will be evaluated by performing an exact binomial test comparing the observed proportion (overall AE free-rate at 5 years) to 92.5%. Equivalently, the two-sided 95% lower confidence bound for the absolute difference between the overall AE free-rate and 92.5% must exceed zero.

The evaluation of primary safety endpoint 2 will be based on the exact, two-sided 95% confidence interval for the observed, individual AE rates at 5 years. The upper bound of these 95% confidence intervals must be less than 1%.

Secondary endpoints 1 and 2, which summarize pacing thresholds, sensing, impedance measurements and shock impedance measurements for the Protego lead, will be reported via standard measures, including means, standard deviations, medians, minimums, and maximums.

Secondary endpoint 3, which includes AEs that were excluded from primary safety endpoint 1, through 5 years post-implant will also be summarized as AE rates together with their associated, exact 95% confidence intervals.

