2.4.3 Missing Data

All possible steps will be taken to minimize missing data in the registry. This includes but is not limited to monitoring of registry forms for completeness and supporting efforts to track and maintain contact with registry subjects during the follow-up period.

The reasons for any missing data in the registry will be documented. BIOTRONIK will examine both missing-data patterns, which describe which values are observed and which are missing, and the missing-data mechanisms, which concerns the relationship between missingness and the values of variables in the registry data set².

For evaluation of the long-term primary registry endpoints (safety endpoints 1 and 2), only subjects who achieve 5 years of follow-up or have experienced an adverse event prior to 5 years will be included in the final evaluation of the associated hypotheses. The secondary endpoint of other AEs at 5 years, excluded from the primary safety analyses, will be analyzed in similar manner. There will be no imputation for these missing adverse event outcomes.

For purposes of Kaplan-Meier survival analyses, described in Section 2.4.2, all AE data on enrolled subjects will be included with follow-up times censored at the time of withdrawal or last completed follow-up visit representing the time of the last known AE status.

² R.J.A. Little and D.B. Rubin, 2002, *Statistical Analysis with Missing Data*, 2nd edition, Wiley and Sons

Secondary endpoints, which include successful sensing and pacing, pacing thresholds, sensing and impedance measurements will be analyzed in two ways. First, all available results will be summarized by scheduled visit through the 5 years of registry follow-up. Secondly, a last value carried forward (LVCF) will be used to estimate the values at the final 5-year follow-up evaluation for subjects who withdraw prior to 5 years.

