APPENDIX A: DEFINITION OF TERMS

AE (Adverse Event) – An unwanted affect detected in participants either implant procedure-related, pulse generator-related, lead-related, or other. The term is used whether or not the effect can be attributed to the leads in the study. For the purposes of this study, the CEC will indicate whether the adverse event relatedness to the Protego lead is: not related, related, possibly related, or unknown.

ACC/AHA – American College of Cardiology/American Heart Association

Cardiac Perforation – Penetration of the lead tip through the myocardium (including microperforation), either clinically suspected or confirmed by chest x-ray, fluoroscopy, echocardiogram, intracardiac electrogram and/or visually.

CEC – Clinical Events Committee

Clinical Failure – Inability of the lead to correctly sense or pace in the heart, not attributable to a mechanical malfunction of the lead or pulse generator that remains unresolved despite reprogramming and/or repositioning.

CFR – Code of Federal Regulations

Conductor Fracture – See Lead Fracture

Confirmed Failure – A lead having clinically relevant characteristics that are outside the performance limits established by BIOTRONIK while implanted and in service, as confirmed by analysis, except for changes in characteristics that are due to induced malfunctions. Lead damage caused during or after explant is not considered a failure.

Chronic Threshold – Chronic threshold is defined as the pacing threshold determined at the subject's 3 month follow-up visit.

eCRF – Electronic Case Report Form

EDC – Electronic Data Capture system

Exit Block – The failure of an intact pacing system to capture the heart because the stimulation threshold exceeds the output of the pacemaker.

Explantation – Surgical removal of a lead during the acute implant stage, whereby the lead has not been chronically implanted and can be easily removed by simple traction.

Extracardiac Stimulation – Clinical observation of inadvertent nerve/muscle stimulation other than cardiac muscle, such as the diaphragm or pectoral muscles.

Extraction of a Lead – Surgical removal of a chronically implanted lead.

Failure to Capture or Loss of Capture – Intermittent or complete failure to achieve cardiac stimulation at programmed output delivered outside of the cardiac refractory period.

High Pacing Threshold – One of the following definitions must be met:

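### The two planned summaries of lead measurements cannot separate lead ageing from attrition; same-lead change from the 3-month value should be added

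*Combined protocol and SAP*

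**What the plan says.** Section 2.1.3 lists the electrical measurements of the Protego lead through 5 years as secondary endpoints 1 and 2, and adds: "There are no formal tests of hypotheses associated with secondary endpoints 1-3". Section 2.4.1 says that they "will be reported via standard measures, including means, standard deviations, medians, minimums, and maximums".

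Section 2.4.3 then gives two analyses. In the first, "all available results will be summarized by scheduled visit through the 5 years of registry follow-up". The second: "Secondly, a last value carried forward (LVCF) will be used to estimate the values at the final 5-year follow-up evaluation", applied to subjects who withdraw before then. The same section promises to examine the patterns and mechanisms of missing data, but names no method and no adjusted analysis.

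On attrition, Section 2.3.1 says that "a maximum loss to follow-up of 10% per year (41% over 5 years) was assumed", covering all exits, "including death, device explants, subject directed withdrawals, physician-directed withdrawals, and loss of contact with the subject".

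A 3-month visit with device evaluation is scheduled for every subject (Section 3.2, Table 4; Section 3.2.4). Appendix A makes that visit the reference for pacing threshold: "Chronic threshold is defined as the pacing threshold determined at the" 3-month visit. Section 10.1.3 uses that reference in the follow-up criterion for a high-threshold adverse event. It is not used in the analysis of secondary endpoints 1 and 2.

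**The concern.** These endpoints ask how the lead behaves electrically over 5 years. A by-visit mean at month 60 describes a different set of people from the mean at month 3. Exits include death and explant, and under Section 3.3.3 a lead that is explanted or capped without a new Protego lead leaves the registry. Leavers may therefore have had different values from the start.

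A rise or fall in the visit means could then be read as lead ageing when no lead has changed, or could mask a real change. LVCF errs in another direction: it freezes early values and so flattens a real trend. It also gives a figure only at 5 years, not a course over time. If the two summaries disagree, no planned analysis decides between them.

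**Working it through.** **The plan's own figures.** Five-year attrition is 1 − 0.9^5 = 0.4095, stated as 41%. Enrolment is 1000/0.9^5 = 1693.5, rounded up to 1694. Both reproduce.

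**Inputs**
- Subjects present at 3 months: n3 = 1694 × 0.9^0.25 = 1650. At 5 years: n5 = 1000. Share leaving after month 3: f = 1 − 0.9^4.75 = 0.394.
- Spread, from the predecessor-lead registry in Section 1.3.1, with the ± figures taken as SDs: 0.33 V, 5.43 mV, 124.8 ohm. No spread is given for shock impedance.
- Not in the documents, so varied: d, the difference between leavers and stayers in SD units, and r, the correlation between a lead's 3-month and 5-year values.

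**Visit means when no lead changes.** The 3-month mean contains leavers and stayers; the 5-year mean contains stayers only. The apparent drift has size f × d.

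| d (assumed) | Shift, SD | Threshold, V | Sensing, mV | Impedance, ohm |
|---|---|---|---|---|
| 0.10 | 0.039 | 0.013 | 0.21 | 4.9 |
| 0.25 | 0.098 | 0.032 | 0.53 | 12.3 |
| 0.50 | 0.197 | 0.065 | 1.07 | 24.6 |

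A reader treating the two tabulated means as independent would form a standard error of √(1/1650 + 1/1000) = 0.0401 SD (0.0132 V). The artefact is therefore about 1 such standard error at d = 0.1 and about 5 at d = 0.5 (0.197/0.0401 = 4.9).

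**LVCF.** Take visits at 0.25, 0.5, 1, 1.5, … 5 years, exit at 10% per year unrelated to drift, and a linear drift. The mean time of the last recorded value is 3.893 years. The share of the 3-month-to-5-year drift that is seen is (3.893 − 0.25)/4.75 = 0.767. About 39% of the 5-year values are carried forward.

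**The three summaries compared.** A simulation of 500 registries with no ageing, leavers 0.5 SD higher and r = 0.7 gave a mean apparent drift of −0.197 SD from visit means, 0.00 from LVCF and 0.00 from paired same-lead change.

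**Precision.** The subjects present at month 60 are also in the 3-month mean, so the fair comparator allows for the overlap. In SD units:
- Paired change: √(2(1 − r)/n5)
- Difference of visit means: √(1/n3 + 1/n5 − 2r/n3)
- Two-visit repeated-measures estimate: √((1 − r²)/n5 + (1 − r)²/n3)

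| r (assumed) | Paired | Visit means | Ratio, paired to visit means | Repeated measures |
|---|---|---|---|---|
| 0 | 0.0447 | 0.0401 | 1.12 | 0.0401 |
| 0.3 | 0.0374 | 0.0352 | 1.06 | 0.0347 |
| 0.5 | 0.0316 | 0.0316 | 1.00 | 0.0300 |
| 0.7 | 0.0245 | 0.0275 | 0.89 | 0.0238 |
| 0.8 | 0.0200 | 0.0252 | 0.79 | 0.0196 |
| 0.9 | 0.0141 | 0.0227 | 0.62 | 0.0140 |

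Setting the first two expressions equal gives r = 0.5 exactly. The repeated-measures estimate is no worse than either at every r shown.

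**The case against.** The strongest defence is that the plan already has an answer to selective attrition. LVCF keeps leavers in, and in the simulation it removed the artefact as fully as pairing did. A reader might infer that the by-visit table is the only analysis; Section 2.4.3 does not support that. What remains is that LVCF brings its own bias, towards no change, and covers only the 5-year point.

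A reader might also infer that the registry never compares a lead with its own earlier value. The follow-up criterion for high pacing threshold does so, requiring a doubling from the 3-month value together with a level above 3.5 V. That is a yes/no event criterion for one parameter, not an estimate of continuous change.

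A third tempting reading is that pairing is always more precise. Against the independent-means standard error (0.0401 SD), pairing looks 21% better at r = 0.5 and 50% better at r = 0.8, but that ignores the overlap. Allowing for it, the gain is 0% and 21%, and below r = 0.5 pairing loses.

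It is also fair to say that shifts of up to 0.065 V or 25 ohm are small beside the abnormality limits in Section 10.1.3, that 41% is a planning maximum, and that no decision depends on a visit mean. Lead failures that are acted on are captured per subject through the adverse-event endpoints and the Kaplan-Meier curves, which keep leavers until censoring. So the documents do not support a claim that lead failure would go undetected. These points limit the consequence. They do not make either planned summary an estimate of how a lead changes.

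**Conclusion.** The point holds as a low-cost improvement. Secondary endpoints 1 and 2 have no planned estimate of continuous same-lead change. At the planned attrition, visit means could shift by about 0.04 to 0.20 SD with no lead changing, and LVCF would show about 77% of a linear drift.

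The first figure rests on an assumed leaver difference of 0.1 to 0.5 SD, on the predecessor lead's spread and on attrition at its planning maximum. The second rests on a linear drift and on exit unrelated to it. The benefit of the change is interpretability; a precision gain from simple pairing depends on a correlation above 0.5 that the documents do not report. The effect is confined to the reading of descriptive endpoints. The primary endpoints and the sample size are untouched.

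**What to change.** In Sections 2.4.1 and 2.4.3, for secondary endpoints 1 and 2:

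- Add same-lead change from the 3-month value at each later visit. Take the mean change and its 95% confidence interval from a repeated-measures mixed model on all available visits, with visit as a factor and the 3-month value among the outcomes. Report percentiles of the observed changes.
- State what happens when one Protego lead replaces another. Section 3.2.5.2 keeps such a subject on the original visit schedule, so change within a subject is not always change within a lead. Censor the series at replacement, or restart it with a named new reference visit.
- Show the 3-month values of completers and leavers side by side, so that the leaver difference assumed above is observed.
- Keep the by-visit table as description and make LVCF a sensitivity analysis.

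The cost is plan wording and one model per parameter, on data already collected. Leads without a 3-month value drop out of the simple change table but still contribute to the model. The model helps where recorded values predict exit. It does not correct for exits caused by deterioration that was never recorded, and the plan should say so.

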3.2.5.1 Protego Related Interim Follow-ups

For unscheduled interim in-office follow-ups related to the Protego lead (but not including a system revision), the data collection and reporting requirements are the same as those required for routine follow-ups (Section 3.2.4).

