3.2.5.2 System Revisions

For interim evaluations that involve a system revision (even if the Protego lead is not directly affected), the following are required:

- Collect implant information
 - o Date of revision
 - o Implant approach/method, and venous access
 - o Implant location of pulse generator and implanted leads
- Record extraction experience (if applicable).
- Collect information on newly implanted system (pulse generator and leads manufacturer/model, serial numbers, etc.).
- Record electrical parameters of the implanted leads. Perform all pacing threshold measurements at 0.4 ms or 0.5 ms pulse width.

-
- Record any lead-related, pulse generator-related and procedure-related adverse events during implant and complete the Adverse Event eCRF.
 - Set programming parameters to best suit the needs of the subject.
 - Complete System Revision and Out of Service (OOS) eCRF, as applicable.

If the Protego lead is replaced with another Protego lead, the subject will continue participation in the registry based on the original implant date and visit schedule. If the Protego lead is explanted and the subject does not receive a new Protego lead, the subject will be withdrawn from the registry. See Section 3.3.3 for details on withdrawals due to lead or pulse generator extraction.

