3.3.3 Protego Lead or Pulse Generator Extraction

Any subject who has the Protego lead explanted or capped, and is not implanted with another Protego lead, will be withdrawn from the registry. Additionally, any subject who has their BIOTRONIK pulse generator explanted and replaced with a non-BIOTRONIK device will also be withdrawn from the registry (even if the Protego lead remains). Only complete a registry exit eCRF after documentation of the system revision procedure (see Section 3.2.5.2) is available. For example, if the Protego lead and pulse generator are explanted due to infection, the subject should not be exited until a non-registry lead/system is implanted or documentation is available stating that the subject will not be re-implanted with a registry qualifying lead/system. Report the exit on the Registry Exit eCRF and any adverse events resulting from the explant procedure.

Whenever possible, devices that are explanted must be returned to BIOTRONIK for analysis.

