7. REGISTRY MONITORING

7.1 SUMMARY

BIOTRONIK's responsibility as the clinical registry sponsor is to ensure protocol and regulatory compliance through proper monitoring of the investigation. BIOTRONIK requires IRB/EC review and a subject Informed Consent Form for all after-market research. Monitoring may be conducted on-site at the investigational site or remotely by BIOTRONIK monitors.

Through on-site or centralized monitoring, BIOTRONIK will assess the site's performance in the following areas:

- Verification that informed consent was obtained and documented properly
- Adherence to protocol eligibility criteria and requirements
- Conduct and documentation of procedures and assessments related to:
 - o Study endpoints
 - o Protocol required safety assessments
 - o Evaluating, documenting, and reporting unanticipated adverse device effects, subject deaths, and withdrawals, especially when a withdrawal may be related to an adverse event.
- Investigator oversight and delegation of authority to study personnel
- Verification of study-specific required documentation
- Conduct and documentation of procedures essential to trial integrity
- Adherence to the applicable FDA regulations regarding the obligations of the investigator and maintenance of records.

As the investigator, the physician is responsible for conducting the registry in accordance with the signed agreement, the investigational plan (protocol), applicable laws, FDA regulations, and any conditions of approval imposed by the reviewing IRB/EC. The principal investigator must also accept responsibility for all aspects of the registry including the actions of any sub-investigators participating in the registry at the investigational site.

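### The carried-forward 5-year summary of lead measurements gives values to explanted or capped leads, and the exits it covers are not defined

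*Combined protocol and SAP*

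**What the plan says.** Section 2.4.3 (Missing Data) gives two summaries for the lead measurements of secondary endpoints 1 and 2. The first uses observed data: "First, all available results will be summarized by scheduled visit through the 5 years of registry follow-up". In the second, "a last value carried forward (LVCF) will be used to estimate the values at the final 5-year follow-up evaluation for subjects who withdraw" before 5 years. No type of withdrawal is excepted.

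Two other sections say what happens when a lead is removed. Section 3.2.5.2: "If the Protego lead is explanted and the subject does not receive a new Protego lead, the subject will be withdrawn from the registry". Section 3.3.3: "Any subject who has the Protego lead explanted or capped, and is not implanted with another Protego lead, will be withdrawn from the registry". A subject whose lead is replaced by another Protego lead stays in the registry (3.2.5.2).

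Section 2.3.1 uses the terms differently. Its attrition figure covers every cause of exit, "including death, device explants, subject directed withdrawals, physician-directed withdrawals, and loss of contact with the subject". Section 3.3.2 handles death as a registry exit and does not call it a withdrawal. Section 3.3.4 says subjects lost to follow-up are exited. Section 2.1.3 states that no hypothesis is tested for these endpoints, and Section 2.4.1 reports them as means, standard deviations, medians, minimums and maximums.

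**The concern.** A 5-year threshold, sensing or impedance value for a lead that was explanted or capped earlier does not exist, so it is not simply missing. Carrying a value forward for that lead puts a number in the 5-year table for a lead that was not in service at 5 years. For other subjects who leave early, the table shows an earlier reading, possibly the implant reading, under a 5-year label.

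There is also a question of reproducibility. The plan does not say whether deaths and losses of contact count as withdrawals, so two analysts could produce different denominators from the same data.

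At stake is how one of two descriptive tables is read, in a registry whose stated purpose includes evaluating acute and chronic lead parameters. The primary endpoints do not use this method.

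**Working it through.** **Step 1: which exits the rule reaches.**

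- Consent withdrawn (3.3.1): a withdrawal, so carried forward.
- Lead explanted or capped with no new Protego lead (3.2.5.2, 3.3.3): called withdrawn, so carried forward as written. Section 2.3.1 lists device explants as a separate category.
- Generator replaced by another manufacturer's device (3.3.3): called withdrawn, although the Protego lead may still be in place.
- Death (3.3.2; listed separately in 2.3.1): not stated. The monitoring list in Section 7.1 also separates the two ("reporting unanticipated adverse device effects, subject deaths, and withdrawals"), but that list is not a definition.
- Loss of contact (3.3.4; listed separately in 2.3.1): not stated.

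**Step 2: reproduce the plan's attrition.** Section 2.3.1: "a maximum loss to follow-up of 10% per year (41% over 5 years) was assumed".

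- Retained at 5 years: 0.9^5 = 0.59049. Exited: 1 − 0.59049 = 0.4095, or 41%.
- Enrolment: 1000 / 0.59049 = 1693.5, rounded up to 1694. Both figures match the plan.

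**Step 3: ceiling on carried-forward values.**

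- Exits: 1694 × 0.40951 = 693.7, about 694. Completers: 1694 × 0.59049 = 1000.3.
- If every exit counts as a withdrawal and has at least one earlier reading: 694 / 1694 = 41%.

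**Step 4: how old the carried values would be.** Assume a constant exit rate and that every visit due before exit was made and measured. Visits fall at implant, 3, 6, 12 and 18 months and so on. A last visit at 12 months or earlier then means exit before 18 months.

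- 1 − 0.9^1.5 = 0.1462, and 1694 × 0.1462 = 247.6, about 248 subjects. That is 248 / 694 = 36% of the carried values.

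**Step 5: dependence on what counts as a withdrawal.** The documents do not split exits by cause, so the share s that counts is an assumption. The carried-forward fraction is 693.7s / (693.7s + 1000.3).

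| Share of exits counted (assumed) | Carried forward / total | Fraction |
|---|---|---|
| 25% | 173 / 1174 | 15% |
| 50% | 347 / 1347 | 26% |
| 75% | 520 / 1521 | 34% |
| 100% | 694 / 1694 | 41% |

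**Step 6: lower attrition.** The plan's 10% is a maximum. With all exits counted:

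- 5% per year (assumed): 1694 × (1 − 0.95^5) = 383, or 23%.
- 2% per year (assumed): 1694 × (1 − 0.98^5) = 163, or 10%.

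**The case against.** The strongest reply is that little depends on this table. It is the second of two descriptive summaries, and the observed by-visit results come first. Section 2.4.3 also commits to documenting reasons for missing data and examining patterns and mechanisms. Lead failures are captured elsewhere: as adverse events (Sections 10.1.3 and 10.3.1), through root-cause investigation (2.4.2), and through extraction and returned-product data (2.1.4). All of this stands and keeps the point minor. None of it corrects the carried-forward table itself.

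A second reply is that Section 2.3.1 lists device explants apart from withdrawals, so the authors may not have meant explants to be carried forward. That is possible, and it shows that the word is used unevenly. But Sections 3.2.5.2 and 3.3.3 say outright that these subjects are withdrawn, and Section 2.4.3 makes no exception.

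Three stronger readings are tempting but not supported:

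- **A known bias in the 5-year values.** The documents give no time course for the measurements. Appendix A defines the chronic threshold at 3 months, which is compatible with little later change in threshold. The high-threshold definition allows for later rises, and neither speaks to sensing or impedance. Neither size nor direction can be stated.
- **A count of out-of-service leads.** The planning event rate of 5% would give 0.05 × 1694, about 85, but it is a rate of primary adverse events. Not all of these end in removal without a new Protego lead, and removals for other reasons are not in it. It is neither an estimate nor a bound.
- **Failing leads' abnormal readings entering through revision visits.** For Protego-related interim visits "the data collection and reporting requirements are the same as those required for routine follow-ups", but Section 3.2.5.1 excludes system revisions. Section 3.2.5.2 does not clearly require a reading of the old lead before removal, and Section 2.4.3 does not say whether unscheduled visits feed the carry-forward.

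**Conclusion.** The point holds as a minor one. As written, the carried-forward summary gives 5-year values to Protego leads explanted or capped without a Protego replacement. That follows from reading Section 2.4.3 with Sections 3.2.5.2 and 3.3.3 and needs no numerical assumption. The term *withdraw* is also not used uniformly, and the treatment of deaths and loss of contact is not stated.

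The 41% is a ceiling. It needs the plan's maximum attrition and every exit counted as a withdrawal. The realistic share could be well below it, as the assumed ranges show. How many carried values belong to explanted or capped leads, and whether the summary is biased, cannot be derived from the documents. No test, sample size or primary endpoint is affected.

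**What to change.** Amend Section 2.4.3 as follows:

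1. Name the observed by-visit summary as the main 5-year result, and show the number of leads measured at each visit.
2. Do not carry values forward past death or past the date the Protego lead leaves service. List the last available readings of those leads in a separate table.
3. Define *withdraw* by exit type, including loss of contact. Label the carried-forward summary as sensitivity only, and report the number of values carried forward by exit reason and by source visit.

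A repeated-measures mixed model is optional and not needed. It would not supply the planned medians, minimums and maximums, and its missing-at-random assumption may fail for leads removed because they malfunctioned.

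The cost is a few sentences of wording, one extra table, and a smaller denominator in the carried-forward summary. The separate table may be sparse, because a reading shortly before removal is not clearly required.
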